5.3.5 Chemistry & Hematology Tests

Chemistry and Hematology tests will be performed as outlined in the tables in Section 5.1 and within 72 hours prior to dosing.

Chemistry tests are to include LFTs (ALT, AST, total bilirubin, alkaline phosphatase), BUN or serum urea level, creatinine, calcium, magnesium, sodium, potassium, bicarbonate, chloride, lactate dehydrogenase (LDH), amylase, lipase and glucose.

Hematology tests are to include a CBC with differential.

Additional measures including non-study required laboratory tests should be performed as clinically indicated. Laboratory toxicities (eg, suspected drug inducted liver enzyme elevations) will be monitored via on site/local labs until all study drug related toxicities resolve, return to baseline or are deemed irreversible. Management algorithms for suspected hepatotoxicity can be found in Appendix 4 of the BMS-936558 (nivolumab) Investigator Brochure and in Appendix 7 of the ipilimumab Investigator Brochure.

5.3.5.1 Thyroid Function Tests

Thyroid function tests will be performed as outlined in Section 5.1.

At Screening, thyroid function testing is to include TSH, free T3, and free T4. At subsequent timepoints, thyroid function testing consists of TSH only. However, if TSH is abnormal reflexive testing of free T3 and free T4 are to be performed. Management algorithms for suspected

endocrinopathy (including abnormal thyroid function) can be found in Appendix 5 of the BMS-936558 (nivolumab) investigator brochure and in Appendix 9 of the ipilimumab investigator brochure.

5.3.5.2 Hepatitis B & C Testing

Hepatitis B (HBV sAG) and Hepatitis C (HCV RNA) testing will be conducted during Screening.

5.3.6 Electrocardiogram (ECG)

All subjects who have met eligibility criteria are required to have a 12-lead ECG performed during Screening. If clinically indicated, additional ECGs may be obtained during the study.

5.3.7 Imaging Assessment for the Study

Not applicable.

5.4 Efficacy Assessments

Study evaluations will take place in accordance with the tables in Section 5. Screening/baseline tumor assessments should be performed within 28 days prior to randomization utilizing CTs/MRI. In addition to chest, abdomen, pelvis, the brain and all known sites of disease should be assessed at screening/baseline. Subsequent assessments should include chest, abdomen, pelvis, and all known sites of disease and should use the same imaging method as was used at screening/baseline.

Change in tumor measurements and tumor responses will be assessed by the investigator using the RECIST (Response Evaluation Criteria in Solid Tumors) 1.1 criteria. For the secondary endpoint of response rate at Week 25, each subject's response at Week 25 will be evaluated in relation to baseline/screening tumor assessment independently of any other tumor assessments (including Week 13 or any unscheduled tumor assessments).

In the **Induction Period**, tumor assessments will be performed after the last dose in Induction Period 1 and prior to the first dose in Induction Period 2 (Week 13 +/- 1 week) and after the last dose in Induction Period 2 and prior to the first dose in the Continuation Period (Week 25 +/- 1 week). Brain scans are required at prior to dosing on Week 13 and Week 25.

In the **Continuation Period**, tumor assessments will be performed prior to dosing on Weeks 33 and 41 (+/- 1 week) and then every 12 weeks (prior to dosing) starting on Week 49 (+/- 1 week). If there are known brain lesions, brain scans should be done with the tumor assessments as indicated above. If there are no known brain lesions, brains scans are only required every 24 weeks beginning at Week 49.

In the **Follow-Up Period**, tumor assessments are to be performed on subjects that discontinue treatment for reasons other than progressive disease. Tumor assessments will be performed prior to dosing at Weeks 33 and 41 (+/- 1 week), then every 12 weeks (prior to dosing) starting on Week 49 (+/- 1 week) until progressive disease, withdrawal of study consent, subject is lost to follow-up, or start of a subsequent anti-cancer therapy. If there are known brain lesions, brain scans should be done with the tumor assessments as indicated above. If there are no known brain

Revised Protocol No.: 01

lesions, brains scans are only required every 24 weeks beginning at Week 49 (brain scan is required at Week 49).

Tumor assessments **must not** be delayed until X01 or X02.

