3.1.2 Treatment Phase (Induction Period 1, Induction Period 2, Continuation Period)

- Begins with the randomization call to the IVRS. The subject is randomly assigned to either Cohort A or Cohort B.
- Doses of either nivolumab or ipilimumab may be omitted if there is an AE which precludes treatment at a scheduled treatment visit (Section 4.3.4.1). Treatment may resume at the next scheduled dose if retreatment criteria (specified in Section 4.3.4.2) are met.
- Dose interruptions will be allowed for infusion reactions, according to guidelines in Section 4.3.4.3.
- Tumor biopsies (Section 5.6.1) must be performed at Week 13 and time of disease progression, unless the designated lesion(s) have responded during study treatment and are no longer accessible for biopsy.
- Treatment Phase ends when subject completes or discontinues all study dosing.

3.1.2.1 Induction Period 1

• Induction Period 1 begins at Week 1, Day 1. Induction Period 1 is the first 12 weeks of study treatment (Week 1 to Week 13). Subjects must receive the first dose of study treatment within 3 working days following randomization.

- Subjects in Cohort A will receive nivolumab at a dose of 3 mg/kg as a 60 minute IV infusion every 2 weeks (14 days) for up to 6 doses.
- Subjects in Cohort B will receive ipilimumab at a dose of 3 mg/kg as a 90 minute IV infusion every 3 weeks (21 days) for up to 4 doses.
- Study assessments will be conducted as outlined in Table 5.1-2 and Table 5.1-3.
- Tumor biopsies (Section 5.6.1) must be performed prior to dosing at Week 13, unless the designated lesion(s) have responded during study treatment and are no longer accessible for biopsy.
- All subjects must have tumor assessment performed at Week 13 (prior to the first dose in Induction Period 2). This includes any subject who may have discontinued treatment prior to receiving all planned Induction Period 1 doses.
- Subjects who have clinical or radiographic progressive disease prior to the completion of Induction Period 1 are to remain on their current study treatment for the remainder of Induction Period 1, provided they are tolerating study treatment and do not have rapid clinical deterioration.

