3.1.3 Follow-Up Period

- Begins when the decision is made to discontinue a subject from study treatment or the subject has completed 2 years of study therapy from the first study treatment in Induction Period 1 (no further treatment with either nivolumab or ipilimumab)
- For subjects who have NOT progressed, tumor assessments will continue as scheduled at Weeks 13, 25, 33, 41 and then starting at Week 49 every 12 weeks until documented progression.
- Subjects will be followed for all toxicities until these toxicities resolve, return to baseline or are deemed irreversible. All AEs will be documented for a minimum of 100 days after last dose of study treatment.

After completion of the two "X" follow-up visits (Table 5.1-5) subjects will be followed every 3 months (by clinic visit or telephone contact) for survival and report of any subsequent anti-cancer treatments for up to 5 years from the first dose of study treatment in Induction Period 1 until death, loss to follow-up, or withdrawal of consent.

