8.3.2 Secondary Endpoints

Secondary endpoints will be analyzed at the time of the primary endpoint analysis. Duration of response from Week 25 will be re-assessed at time of the OS update analysis.

8.3.2.1 Response Rate at Week 25

Response rate at Week 25 is defined as the number of subjects who have a complete response (CR) or partial response (PR) at Week 25, with confirmation at scheduled scan at Week 33, divided by the total number of randomized subjects. Note that the results of the tumor assessment at Week 13 will not be considered in the assessment of response rate at Week 25. This means, for example, that subjects with progressive disease at Week 13 are not precluded from having an assessment of CR or PR at Week 25 for this endpoint if the scan at Week 25 demonstrates such a response.

Duration of response (DOR) from Week 25 will also be assessed for subjects with confirmed response at Week 25 (see definition above). DOR is defined as the time between the Week 25 assessment date and the date of objectively documented disease progression (taking as reference

the smallest sum of diameters of target lesions beginning at Week 25) or death, whichever occurs first.

8.3.2.2 Progression Rates at Weeks 13 and 25

Progression rate at a specific timepoint is defined as the number of subjects who have Progressive Disease (PD) per RECIST 1.1 at that specific timepoint divided by the total number of randomized subjects.

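### The Follow-Up imaging rules contradict each other and do not secure the Week 33 scan that the Week 25 response rate needs for confirmation

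*Protocol*

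**What the plan says.** **Endpoint.** Under Protocol 5.4, each subject's "response at Week 25 will be evaluated in relation to baseline/screening tumor assessment independently of any other tumor assessments". Section 8.3.2.1 adds that "subjects with progressive disease at Week 13 are not precluded from having an assessment of CR or PR at Week 25 for this endpoint". A response is counted only "with confirmation at scheduled scan at Week 33, divided by the total number of randomized subjects". Duration of response (DOR) from Week 25 is assessed in confirmed responders only, with progression measured from "the smallest sum of diameters of target lesions beginning at Week 25".

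**Scans during induction.** Section 3.1.2.1 is explicit: "All subjects must have tumor assessment performed at Week 13". Section 3.1.2.2 makes the Week 25 scan mandatory in the same way, including for subjects already off treatment. No equivalent sentence covers Week 33.

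**Scans in Follow-Up.** Three places give the rule:
- Section 3.1.3, in a sentence restricted to those without progression so far: "tumor assessments will continue as scheduled at Weeks 13, 25, 33, 41 and then starting at Week 49 every 12 weeks until documented progression".
- Section 5.4: "tumor assessments are to be performed on subjects that discontinue treatment for reasons other than progressive disease", continuing "until progressive disease, withdrawal of study consent, subject is lost to follow-up, or start of a subsequent anti-cancer therapy".
- Table 5.1-5 lists Weeks 25, 33, 41 and 49 with no condition on progression. Its note refers to 5.4, and 5.4 in turn opens by referring to the Section 5 tables.

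**The concern.** The endpoint deliberately ignores progression (PD) before Week 25, but the Follow-Up imaging rules do not. A subject can therefore be a Week 25 responder by the endpoint's definition and a progressed subject by the imaging rule. If such a subject is off treatment, whether the confirming scan is taken depends on which passage the site follows, or on why treatment stopped, and not on the tumor.

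A responder without a Week 33 scan stays in the denominator as a non-responder. Because the response is unconfirmed, the subject also never enters the DOR analysis. No later analysis document can recover a scan that was not taken, so the imaging instruction has to be right in the protocol.

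**Working it through.** **Step 1. Can such subjects occur?** Section 5.4.4 sets partial response (PR) at a fall of at least 30% from baseline. It sets PD at a rise of at least 20% and at least 5 mm from the smallest sum on study. The sums below are invented to show that the routes exist.

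*Subject 1, Cohort B:* 100 mm at baseline, 130 mm at Week 13, 65 mm at Week 25.
- Week 13: 130/100 − 1 = +30% (+30 mm), PD.
- Week 25: 65/100 − 1 = −35%, PR.
- Nivolumab was permanently stopped for toxicity in Induction Period 2, so under 4.3.6.2 there is no Continuation treatment and the subject is in Follow-Up.

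*Subject 2, Cohort B:* 100 mm at baseline, 40 mm at Week 13, 65 mm at Week 25.
- Week 25 against baseline: −35%, PR for the endpoint.
- Week 25 against nadir: 65/40 − 1 = +62.5% (+25 mm), PD.
- Section 3.1.2.3 allows the investigator to stop treatment in a Cohort B subject with no PD at Week 13 and PD at Week 25.

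**Step 2. Is the Week 33 scan ordered?**

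| Subject | 3.1.3 | 5.4 | Table 5.1-5 |
|---|---|---|---|
| 1: PD at Week 13, PR at Week 25, stopped for toxicity | No | Plausibly yes: the reason for stopping was not PD, although the end rule at PD leaves doubt | Yes |
| 2: PR against baseline, PD against nadir, stopped for that PD | No | No | Yes |

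The three places agree for neither subject. For Subject 2, both text sections end imaging and only the table orders it.

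**Step 3. What does one lost confirmation cost?** The protocol uses Clopper-Pearson limits for the response rate: lower = Beta quantile (0.025; x, n − x + 1), upper = Beta quantile (0.975; x + 1, n − x). As a check, this reproduces the upper limits in Table 8.1-1 at n = 40: 46.5% for 12, 49.1% for 13 and 51.7% for 14.

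One subject is 1/40 = 2.5 points. Taking 14 confirmable responders and 0 to 3 losses as assumptions:

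| Counted | Rate | Exact 95% CI |
|---|---|---|
| 14/40 | 35.0% | 20.6–51.7 |
| 13/40 | 32.5% | 18.6–49.1 |
| 12/40 | 30.0% | 16.6–46.5 |
| 11/40 | 27.5% | 14.6–43.9 |

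**Step 4. Does the planned sensitivity analysis help?** No. Section 8.4.3.1 restricts it to subjects with a Week 25 scan. The affected subjects have that scan, so they remain non-responders there too.

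**The case against.** **The protocol intends these scans.** Table 5.1-5 lists Week 33 without restriction. Sections 3.1.4 and 8.3.1 wait for treated Week 25 responders to be followed through Week 33. Section 5.4.6.2 says that the Week 33 scan may confirm the response, which is softer than 8.3.2.1. This shows intent and stands as such. But the waiting rule sets the timing of the analysis and orders no scan, and the table refers back to the section that restricts scanning.

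**Subject 1 is largely covered.** This also stands in part. The sentence quoted from 5.4 turns on the reason for stopping; the limit to subjects who have not progressed is in 3.1.3. A reader might infer that no off-treatment responder with earlier PD can be confirmed. The documents do not support that: a toxicity stop is plausibly scanned under 5.4 and the table.

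**Subject 2 is rare, and confirmation is doubtful.** The tumor is growing from nadir, treatment has stopped, and a sum of 70 mm or less would be needed at Week 33. Often no confirmed response would be lost.

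**The size can easily be inflated.** A reader might multiply assumed rates, such as 50% PD at Week 13, 20% response among these and 50% of those off treatment. That gives 40 × 0.50 × 0.20 × 0.50 = 2.0 subjects per cohort and a chance of at least one of 1 − 0.95^40 = 87%. None of these rates is in the protocol. The product also treats every off-treatment responder as unscanned and otherwise confirmable. If, again by assumption, half were scanned anyway and 80% would confirm, it falls to 2.0 × 0.5 × 0.8 = 0.8 subjects and 1 − 0.98^40 = 55%. Neither result is an estimate for this trial.

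**DOR.** A reader might infer that these subjects are in the DOR analysis with truncated follow-up. They are not: DOR covers confirmed responders only, so they are absent from it.

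**Conclusion.** The contradiction is in the text and should be reconciled. Section 3.1.3 read as written withholds the Week 33 scan from a Week 25 responder with earlier PD who is in Follow-Up. Sections 3.1.3 and 5.4 together withhold it from one stopped for PD against nadir. Both conflict with Table 5.1-5 and with the endpoint in 8.3.2.1.

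The number affected is not given and is probably small. The cost is 2.5 points at N = 40 for each subject whose response would have been confirmed, against an interval about 31 points wide at 14/40. The loss could differ between cohorts, because the ways off treatment in 3.1.2.3 and 4.3.6.2 differ by sequence, but the documents give no basis for a direction or amount. This is a correctable flaw in the data collection for one secondary endpoint and its DOR. The primary endpoint and subjects treated in Continuation are not affected.

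**What to change.** Change imaging only, by aligning 3.1.3 and 5.4 with Table 5.1-5 and 8.3.2.1. Suggested sense:

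- Every subject with a complete or partial response at Week 25 against baseline has the scheduled Week 33 scan, whatever the reason for stopping treatment and whether or not PD was recorded at or before Week 25. The exceptions are withdrawal of consent, loss to follow-up and start of subsequent anti-cancer therapy.
- For responders confirmed at Week 33, later scheduled scans continue until progression against the smallest sum from Week 25, as the DOR definition requires, with the same exceptions.

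The cost is about one sentence in each section. Table 5.1-5 already lists the scans, so the schedule does not grow. The downside is that a few subjects are scanned after a PD call, and those who start other therapy before Week 33 remain unconfirmed. A count of Week 25 responders without a Week 33 scan, and a bounding rate that treats them as responders, can be left to the SAP. The Week 25 progression rate stays on RECIST 1.1, and no treatment rule changes.

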- Subjects who do not receive all planned doses in Induction Period 1, including those who discontinue Induction Period 1 treatment early due to progression or discontinuation criteria (Section 4.3.6.2), are to continue their scheduled study assessments (as per Table 5.1-2 and Table 5.1-3) and are still eligible to receive the alternative treatment in Induction Period 2, starting at Week 13.
- After completion of Induction Period 1, subjects will proceed to Induction Period 2, regardless of the results of the tumor assessment at the end of Induction Period 1.

3.1.2.2 Induction Period 2

- Induction Period 2 begins at Week 13 and continues to Week 25.
 - Subjects in Cohort A will receive ipilimumab at a dose of 3 mg/kg as a 90 minute IV infusion every 3 weeks (21 days) for up to 4 doses.
 - Subjects in Cohort B will receive nivolumab at a dose of 3 mg/kg as a 60 minute IV infusion every 2 weeks (14 days) for up to 6 doses.
- Subjects with drug-related AEs after the last dose in Induction Period 1 who fail to meet retreatment criteria (Section 4.3.4.2) at Week 13 will still begin Induction Period 2 at Week 13 and require omission of the initial dose(s) in Induction Period 2 until retreatment criteria are met.
- Study assessments will be conducted as outlined in Table 5.1-2 and Table 5.1-3.
- All subjects, including those who discontinue study treatment prior to receiving all planned doses during Induction Period 2, must have a tumor assessment at Week 25 (after the last dose of Induction Period 2 and prior to the first dose of the Continuation Period).
- Subjects who have clinical or radiographic progressive disease prior to the completion of Induction Period 2 are to remain on their current study treatment for the remainder of Induction Period 2, provided they are tolerating study treatment and do not have rapid clinical deterioration

• Subjects who do not receive all planned treatment doses in Induction Period 2, including those who discontinue Induction Period 2 treatment early due to progression or discontinuation criteria in Section 4.3.6.2, are to continue their scheduled study assessments (as per Table 5.1-2 and Table 5.1-3) and may still be eligible to receive treatment in the Continuation Period, starting at Week 25.

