Adverse Events Assessments	X	[X]	Section 6. Beyond 100 days from the last dose of study therapy, subjects will be followed for ongoing drug-related adverse events until resolved, return to baseline, or deemed irreversible OR until lost to follow-up, withdrawal of study consent, or start of a subsequent anti-cancer therapy.		
Chemistry & Hematology	X		Section 5.3.5.		
Thyroid Function Testing	X		Section 5.3.5.1.		
Efficacy Assessments	•				
Tumor Assessment (CT/MRI)	Week 25, 33, 41 & 49. After Week 49: every 12 weeks	[X]	Section 5.4. To be performed prior to dosing. Scans may be done within 1 week of target week. At Week 25, Chest, abdomen, pelvis & brain required. At Week 33 & 41. Chest, abdomen, pelvis required. Brain scans should be done with tumor assessments, if there are known brain lesions. At Week 49, Chest, abdomen, pelvis and brain scan required. Beginning at Week 49, if there are no known brain lesions, brain scans required every 24 weeks.		

Table 5.1-5: Follow-Up & Survival Period (Cohort A & Cohort B)							
Procedure	Initial Follow-Up Phase Follow-Up Visits 1 (X01) and 2 (X02) ^a	Survival (Y) Follow-Up Visits b Every 3 months	Notes				
Subject Status	X	X	Collection of survival information every 3 months until death, lost to follow-up, or withdrawal of study consent. May be performed by phone contact or office visit.				

a X visits occur as follows: X01 = 30 days from last dose +/- 7 days. X02 = 70-84 days from X01.

^b Y, survival visits occur every 3 months after X visits.

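### The Section 5 Follow-Up imaging schedules omit Week 13 (Table 5.1-5) and Weeks 13 and 25 (5.4 text), contradicting Section 3, which requires both endpoint scans

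*Protocol*

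**What the plan says.** Section 3 of the protocol is consistent with itself. Section 3.1.2.1 states: "All subjects must have tumor assessment performed at Week 13 (prior to the first dose in Induction Period 2"). It adds: "This includes any subject who may have discontinued treatment prior to receiving all planned Induction Period 1 doses". Section 3.1.2.2 applies the same rule to everyone at the second timepoint, in these words: "including those who discontinue study treatment prior to receiving all planned doses during Induction Period 2, must have a tumor assessment at Week 25". Section 3.1.3, on Follow-Up, says of those without progression: "tumor assessments will continue as scheduled at Weeks 13, 25, 33, 41 and then starting at Week 49 every 12 weeks until documented progression".

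Section 5 differs in two places.

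- The tumor-assessment row of Table 5.1-5 (Follow-Up and Survival) reads "Week 25, 33, 41 & 49. After Week 49: every 12 weeks". Week 13 is absent.
- The Follow-Up paragraph of 5.4 says that "tumor assessments are to be performed on subjects that discontinue treatment for reasons other than progressive disease", and gives the timing as "Tumor assessments will be performed prior to dosing at Weeks 33 and 41 (+/- 1 week), then every 12 weeks (prior to dosing"). Weeks 13 and 25 are both absent.

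Section 5.4 opens with "Study evaluations will take place in accordance with the tables in Section 5", and Section 3.5 sends subjects who have stopped investigational product to the Section 5 procedures.

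**The concern.** Under 3.1.3, Follow-Up starts as soon as the decision to stop study treatment is made. A subject who stops both drugs during induction, for example under 4.3.6.1, can therefore be in Follow-Up before Week 13 or Week 25. The Follow-Up material in Section 5 is what a site would naturally consult for that subject, and it does not list every scan that Section 3 requires.

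Three secondary rates are at stake: progression at Week 13, progression at Week 25 and response at Week 25. Each belongs to a fixed timepoint, so a later scan does not replace a missed one. Subjects who stop everything early without progression include those who stop for toxicity. Toxicity may differ between the two sequences, so any loss of scans may also differ between cohorts.

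**Working it through.** **Step 1. The schedules side by side.**

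| Source | Subjects covered | Week 13 | Week 25 | Week 33 onward |
|---|---|---|---|---|
| 3.1.2.1 | all, including early discontinuers | required | not its subject | not its subject |
| 3.1.2.2 | all, including early discontinuers | not its subject | required | not its subject |
| 3.1.3 | Follow-Up, not progressed | listed | listed | listed |
| Table 5.1-5 | Follow-Up | **absent** | listed | listed |
| 5.4, Follow-Up paragraph | Follow-Up, stopped for reasons other than PD | **absent** | **absent** | listed |

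For Week 13, both Section 5 Follow-Up sources disagree with Section 3. For Week 25, only the 5.4 paragraph does.

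The omissions look like reused text. The row in Table 5.1-5 has the same weeks as the row in Table 5.1-4 for the Continuation Period. Both Follow-Up entries also time scans relative to dosing, although these subjects receive no further doses. A schedule meant for subjects already past Week 25 appears to have been applied to subjects who leave earlier.

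**Step 2. Who is exposed.** Subjects who stop only the current drug and remain eligible for the next period stay on Tables 5.1-2 and 5.1-3 (3.1.2.1 and 3.1.2.2), and both tables carry the Week 13 scan. The exposed group is subjects who stop all study treatment without progression before Week 13 or, by the 5.4 text alone, before Week 25. Whether subjects who leave because of progression should still be scanned is a separate question and is not counted here.

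**Step 3. What a missed scan does to the estimate.**

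- With no imaging at a timepoint, the subject is NE there (5.4.6.1).
- The denominator of all three rates is all randomized subjects (8.3.2.1, 8.3.2.2).
- The numerator needs PD at the timepoint, or CR/PR at Week 25 with confirmation at Week 33.

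So the NE subject counts in the denominator only. Let x be the number of observed events and N the number randomized in the cohort. One missed scan in a subject who would have had the event changes the rate from (x + 1)/N to x/N, a loss of 1/N. With N = 40 (8.1), 1/40 = 2.5 percentage points. If the subject would not have had the event, the loss is zero. Hence the loss is up to 2.5 points per missed scan, and slightly less per scan if more than 40 are randomized.

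The Week 13 omission affects only the Week 13 progression rate, because 8.3.2.1 sets the Week 13 result aside when judging Week 25 response. The Week 25 omission in 5.4 could affect both Week 25 rates.

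**Step 4. How many scans might be missed.** The only related figure is the allowance in 8.1 of at most 12.5% drop-out in Induction Period 1. It reproduces: 40 x (1 - 0.125) = 35, so at most 5 of 40 leave. It covers drop-out for every reason and so does not give the number of exposed subjects.

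**Step 5. What the planned analyses would show.** Section 8.4.3.1 includes a sensitivity analysis of Week 25 response in subjects with a Week 25 scan. Section 8.4.3.3 states no such analysis for the progression rates.

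**The case against.** The strongest reply is that the scans are scheduled. Sections 3.1.2.1 and 3.1.2.2 name early discontinuers expressly, 3.1.3 is itself a Follow-Up section and lists both weeks, the Synopsis lists both weeks, and the Induction paragraph of 5.4 gives both with a one-week window. A reader comparing only Table 5.1-5 with the 5.4 Follow-Up paragraph might infer that early leavers have no scheduled scan at the endpoint timepoints. The documents do not support that. The objection stands on this, and what remains is a contradiction rather than an absent requirement. The Induction paragraph does not remove the contradiction, because it ties the scans to the last dose of one period and the first dose of the next, and a subject off all treatment has no such next dose.

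The Week 25 limb is the weaker one. Section 5.4 defers to the tables, and Table 5.1-5 lists Week 25, so a site would have to follow one paragraph against every other source. This also stands.

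A reader might also size the effect by taking all 5 subjects in the 12.5% allowance as missing a scan and assuming how many had progressed. That does not hold. The allowance includes progression, death and withdrawal as well as stopping without progression, no PD count is given, and nothing shows that every such subject would miss a scan that Section 3 requires. Nor do all toxicity stoppers fall in the gap, since many remain on the induction tables.

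Finally, the evaluable-only analysis partly covers Week 25 response. It does not restore missing scans, and the protocol states no counterpart for progression.

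**Conclusion.** The point holds as an internal inconsistency. The tumor-assessment row of Table 5.1-5 and the Follow-Up paragraph of 5.4 are wrong as written when set against 3.1.2.1, 3.1.2.2 and 3.1.3. Week 13 is the stronger limb, because both Section 5 Follow-Up sources omit it and the protocol states no evaluable-only analysis for the progression rates.

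The supportable size is up to 2.5 points on the affected rate per missed scan, assuming 40 randomized per cohort and that the subject would have had the event. The total cannot be given: the number of missed scans is not in the protocol, and it is zero if sites follow Section 3. The exposed group is small, namely subjects who stop all treatment before the timepoint without progression. The primary safety endpoint is not affected.

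**What to change.** Reconcile the passages in an amendment:

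1. Add Week 13 to the tumor-assessment row of Table 5.1-5.
2. Add Weeks 13 and 25 to the Follow-Up paragraph of 5.4.

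Both entries then match 3.1.2.1, 3.1.2.2 and 3.1.3. The cost is two wording changes. Section 3 already requires these scans, so there is no new procedure and no added burden for subjects.
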